1.2. Estimands

1.2.1. Primary Estimand

The primary clinical question of interest is: What is the impact of MTD of tirzepatide (10 mg or 15 mg) QW, compared with placebo, on the maintenance of weight loss after an initial 36-week open-label tirzepatide lead-in treatment period, in study participants who do not have T2DM, and have obesity ($\text{BMI} \geq 30 \text{ kg/m}^2$) or are overweight ($\text{BMI} \geq 27 \text{ kg/m}^2$) with at least 1 weight-related comorbid condition?

For primary disclosure of Study GPHN including submission to the US FDA

The estimand is described by the following attributes:

- Population: patients qualifying for study entry per protocol inclusion/exclusion criteria who reach and tolerate either tirzepatide 10-mg or 15-mg dose at Visit 11(Week 36).
- Endpoint: percent change in body weight from randomization (Week 36) to 88 weeks.
- Treatment condition of interest: tirzepatide MTD versus placebo, regardless of study drug adherence.
- Handling of intercurrent events (ICEs): The ICEs leading to treatment discontinuation for any reason are addressed by the treatment condition of interest attribute and handled by

treatment policy strategy as described in the International Council for Harmonisation (ICH) E9 (R1) Addendum (ICH 2019). Further details can be found in Section 4.3.2.3.

- Population-level summary: difference in mean between treatment conditions.

Rationale for estimand: the primary estimand was requested by US FDA; it aims at reflecting how participants are treated in clinical practice, irrespective to the compliance to planned course of treatment.

This *de facto estimand* is referred as the “treatment regimen” estimand in the latter sections of this document, which is equivalent to the “hybrid” estimand in the protocol.

For all other purposes

The estimand is described by the following attributes:

- Population: patients qualifying for study entry per protocol inclusion/exclusion criteria who reach and tolerate either tirzepatide 10-mg or 15-mg dose at Visit 11(Week 36).
- Endpoint: percent change in body weight from randomization (Week 36) to 88 weeks.
- Treatment condition of interest: tirzepatide MTD versus placebo, excluding data after discontinuation of study drug.
- Handling of ICEs: The ICEs leading to treatment discontinuation for any reason are addressed by the treatment condition of interest attribute and handled by the hypothetical strategy as described in the ICH E9 (R1) Addendum (ICH 2019).
- Population-level summary: difference in mean between treatment conditions.

Rationale for estimand: this estimand aims at reflecting treatment efficacy in an envisaged scenario in which the intercurrent events leading to treatment discontinuation would not occur.

We will refer to this estimand as “efficacy” estimand in the latter sections.

1.2.2. Estimands for Secondary Endpoints

Table GPHN.1.2. Attribute Description of Secondary Estimands

Secondary Estimand	Population	Endpoint	Treatment condition of interest	Handling of intercurrent events	Population-level summary
Key secondary related to mean change	Same as primary estimand	As described in Table GPHN.1.1	For primary disclosure of Study GPHN including submission to the US FDA, follow the same manner of the treatment regimen estimand in Section 1.2.1; for all other purposes, the same manner of the efficacy estimand in Section 1.2.1	For primary disclosure of Study GPHN including submission to the US FDA, follow the same manner of the treatment regimen estimand in Section 1.2.1; for all other purposes, follow the same manner of the efficacy estimand in Section 1.2.1	Difference in mean changes between treatment conditions
Key secondary related to percentage of participants meeting certain criteria					Difference in percentage of participants between treatment conditions as assessed by odds ratio
Key secondary related to time to meet certain criteria					Difference in time to response between treatment conditions
Additional secondary related to mean change	Same as primary estimand	As described in Table GPHN.1.1	Follow the same manner of the efficacy estimand in Section 1.2.1	Follow the same manner of the efficacy estimand in Section 1.2.1	Difference in mean changes between treatment conditions
Additional secondary related to percentage of participants meeting certain criteria					Difference in percentage of participants between treatment conditions as assessed by odds ratio

Abbreviation: FDA = Food and Drug Administration.

[figure not shown]
Unless otherwise specified, the attributes of estimands supporting exploratory objectives will follow the same manner of the efficacy estimand in Section 1.2.1, with the exception of endpoints and population-level summary, which will be objective specific.

1.3. Study Design

Study GPHN is a Phase 3, multicenter, randomized, parallel-arm, double-blind, placebo-controlled, 88-week study that will investigate the impact of MTD of tirzepatide (10 mg or 15 mg QW), compared with placebo, on the maintenance of weight loss after an initial 36-week open-label tirzepatide lead-in treatment period, in study participants who do not have T2DM, and have obesity ($\text{BMI} \geq 30 \text{ kg/m}^2$) or are overweight ($\text{BMI} \geq 27 \text{ kg/m}^2$) with at least 1 weight-related comorbid condition, excluding diabetes mellitus.

Study GPHN will consist of 4 periods: a 2-week screening period; a 36-week open-label tirzepatide lead-in treatment period (including a 20-week dose-escalation period); a 52-week double-blind, placebo-controlled treatment period; and a 4-week safety follow-up period. The study participants will be randomized in a double-blind 1:1 ratio (tirzepatide MTD QW or placebo) at the end of the open-label lead-in treatment period. Assignment to treatment groups will be determined by a computer-generated random sequence using the IWRS. An upper limit of 70% enrollment of women will be used to ensure a sufficiently large sample of men.

The randomization will be stratified by country, sex (female, male), tirzepatide MTD dose at 36 weeks (10 mg versus 15 mg), and percent weight loss at 36 weeks (<10% versus $\geq 10\%$). Where necessary to be included as a stratification factor, countries with fewer than 10 randomized participants will be pooled into 1 category (pooled country).

Abbreviations: MTD = maximum tolerated dose; QW = once weekly; (T) = telephone visit.

Figure GPHN.1.1. Illustration of study design for Clinical Protocol I8F-MC-GPHN.

The details about the overview of study periods and study visits can be found in Study GPHN protocol Section 4. Details of the unique visits not displayed in [Figure GPHN.1.1](#) are provided below.

Visit 99

Visit 99 is only applicable to participants who discontinue the double-blind study treatment prematurely (after Week 36 and before Week 88) and decline to complete the remaining scheduled study visits. These participants will be asked to return for Visit 99 at 88 weeks ± 7 days. This visit is critical to ensure complete data collection for the primary body weight endpoint.

Early Discontinuation of Treatment Visit

Participants unable or unwilling to continue the study treatment for any reason will perform an ED visit at the visit when the participant informs the site about the study treatment discontinuation. If the participant is discontinuing during an unscheduled visit or a scheduled visit, that visit should be performed as an ED visit.

2. Statistical Hypotheses

The primary objective is to demonstrate that tirzepatide MTD is superior to placebo for percent change from randomization in body weight at Week 88. Thus, the alternative hypothesis to be tested in relation to the primary estimand is as follows:

H1(wgt_pchg_wk36): QW tirzepatide MTD is superior to placebo for percent change from randomization (Week 36) in body weight at 88 weeks.

The alternative hypotheses for the key secondary objectives controlling for type 1 error rate are the following:

H2(wgt_chg_wk36): QW tirzepatide MTD is superior to placebo for change from randomization (Week 36) in body weight (kg) at 88 weeks.

H3(wc_chg_wk36): QW tirzepatide MTD is superior to placebo for change from randomization (Week 36) in waist circumference (cm) at 88 weeks.

H4(maintain80): QW tirzepatide MTD is superior to placebo for percentage of participants who maintain $\geq 80\%$ of the body weight lost during the open-label lead-in period at 88 weeks.

H5(return95): QW tirzepatide MTD is superior to placebo for delaying time (in weeks), during the 52-week double-blind treatment period, to first occurrence of participants returning to $>95\%$ Visit 2 (Week 0) body weight among participants who lost $\geq 5\%$ body weight during the open-label lead-in period.

H6(wgt5_wk0): QW tirzepatide MTD is superior to placebo for percentage of participants who achieve $\geq 5\%$ body weight reduction from Visit 2 (Week 0) at 88 weeks.

H7(wgt10_wk0): QW tirzepatide MTD is superior to placebo for percentage of participants who achieve $\geq 10\%$ body weight reduction from Visit 2 (Week 0) at 88 weeks.

H8(wgt_pchg_wk64): QW tirzepatide MTD is superior to placebo for percent change from randomization (Week 36) in body weight at 64 weeks.

H9(wgt15_wk0): QW tirzepatide MTD is superior to placebo for percentage of participants who achieve $\geq 15\%$ body weight reduction from Visit 2 (Week 0) at 88 weeks.

H10(wgt20_wk0): QW tirzepatide MTD is superior to placebo for percentage of participants who achieve $\geq 20\%$ body weight reduction from Visit 2 (Week 0) at 88 weeks.

2.1. Multiplicity Adjustment

The type 1 error rate control strategy for primary and key secondary efficacy objectives is documented in [Figure GPHN.2.1](#). Both efficacy estimand and treatment regimen estimand will be used to assess those objectives. As they are intended for different purposes, no multiplicity adjustments will be made for conducting separate analyses relative to the efficacy and treatment regimen estimands. In addition, no multiplicity adjustments will be made for evaluating additional secondary and exploratory objectives and safety assessments.

[figure not shown]

Figure GPHN.2.1. GPHN type 1 error control strategy for primary and key secondary efficacy endpoints.

3. Analysis Sets

For purposes of analyses, [Table GPHN.3.1](#) defines the analysis population and analysis sets.

Table GPHN.3.1. Description of Analysis Population and Analysis Datasets

Population/Analysis Set	Description
Entered	All participants who sign informed consent.
Enrolled	All participants who are assigned to open-label tirzepatide treatment.
Randomized	All participants who are randomly assigned a study treatment (double-blind).
Modified Intent-to-Treat (mITT)	All enrolled participants who are exposed to at least 1 dose of study drug.
Efficacy Analysis Set (EAS)	Data obtained during double-blind treatment period from mITT, excluding data after discontinuation of study drug (last dose date + 7 days).
Full Analysis Set (FAS)	Data obtained during double-blind treatment period from mITT, regardless of adherence to study drug.
Safety Analysis Set (SS)	Data obtained during double-blind treatment period and safety follow-up period from mITT, regardless of adherence to study drug.

Unless otherwise specified, for analyses guided by the treatment regimen estimand, FAS will be used. For analyses guided by the efficacy estimand, EAS will be used, and for safety analysis, SS will be used.

For open-label period analysis, the analysis set is defined in Section [6.4.1](#).

For immunogenicity analysis, the analysis set is defined in Section [4.6.5.5](#).

4. Statistical Analyses

4.1. General Considerations

Statistical analysis of this study will be the responsibility of Lilly or its designee. Some analyses and summaries described in this analysis plan may not be conducted if not warranted by data (eg, few events to justify conducting an analysis). Additional analyses of the data may be conducted as deemed appropriate.

Unless otherwise noted, tests of treatment effects will be conducted at a 2-sided alpha level of 0.05, and the CI will be calculated at 95% 2-sided.

Unless specified otherwise, efficacy and safety will be assessed using the mITT population, and data will be analyzed based on the assigned treatment (ie, not the actual treatment received by the participant). For submission to the US FDA to support the registration of tirzepatide for chronic weight management, the primary efficacy analysis will be conducted using FAS. For other purposes, the efficacy analysis of double-blind treatment period will be conducted using EAS. Safety analysis of double-blind treatment period will be conducted using SS.

Unless otherwise specified, for efficacy-related analyses at 88 weeks, country/pooled country, sex, tirzepatide MTD dose at randomization, percent weight loss at randomization and corresponding baseline value will be used as a covariate.

Summary descriptive statistics for continuous measures will include sample size, mean, SD, median, minimum, and maximum. The analysis model to make comparisons among treatment groups relative to continuous measurements assessed over time will be either ANCOVA or a MMRM.

Kaplan-Meier method will be used for estimation of cumulative event-free survival rates over time, and Cox proportional hazards regression analysis will be used to compare hazards rates among treatments.

Summary statistics for categorical measures (including categorized continuous measures) will include sample size, frequency, and percentages. Logistic regression will be used to examine the treatment difference in binary efficacy outcomes if there is a need to adjust for covariate. Otherwise, Fisher's exact test will be used to examine the treatment difference.

Summary statistics for discrete count measures will include sample size, mean, SD, median, minimum, and maximum.

Unless specified otherwise, for analyses in the double-blind treatment period, baseline is defined as the last nonmissing data collected prior to or at randomization (Week 36); for analyses including data collected in open-label lead-in period, baseline is defined as the last nonmissing data collected prior to or at study enrollment (Week 0).

For some specific safety related parameters, the definition of baseline and postbaseline for double-blind treatment period are specified in [Table GPHN.4.1](#).

The definition of baseline and postbaseline during the open-label lead-in treatment period can be found in [Appendix 4](#).

Table GPHN.4.1. Baseline and Postbaseline Definitions for Safety Outcomes in Double-Blind treatment Period

Analysis Set	Analysis Type	Baseline	Postbaseline
SS	1.1) Treatment-Emergent Adverse Events	Ongoing at the time of the randomization to the double-blind treatment period.	Starts after randomization visit and ends after the whole study period (including off-drug follow-up visit).
SS	1.2) Treatment-Emergent Abnormal Labs ^a , Vital Signs, and ECGs.	Refer to Table GPHN.6.1 for baseline definition.	Postbaseline will be defined as above (1.1). All scheduled and unscheduled measurements will be included.
SS	1.4) Change from Last Baseline to Week xx and to Last Postbaseline for Labs ^a , Vital Signs, and ECGs.	The last scheduled and unscheduled non-missing assessment recorded during the open-label lead-in period.	Postbaseline will be defined as above (1.1). Only scheduled visits will be included. The ED visits are considered scheduled visits.

Abbreviations: ECGs = electrocardiogram; ED = early discontinuation; SS = Safety Analysis Set.

^a Immunogenicity-related analysis is specified in Section [4.6.5.5](#).

For the primary and key secondary efficacy endpoint analyses subject to type 1 error rate control, data for participants with missing values at the 88-week visit (or weight-related measurements at 64-week visit) will be imputed based on the method described in Section [4.3.2.3](#). Otherwise, missing values will not be explicitly imputed except for the parameters with only 1 postbaseline measure during the analysis period per schedule of activity, where LOCF approach will be applied to impute the endpoint when ED measure is available.

End of study participation for a participant will be the earliest of date of death, date of withdrawal from further participation in the study, or date of safety follow-up visit (Visit 801). For participants considered to be lost-to-follow-up, end of study participation will be the date of lost-to-follow-up reported by the investigator. Participant data included in the database after the last date of study participation will be excluded from statistical analysis.

Statistical summaries and results of statistical analyses will be displayed in the following order: placebo, tirzepatide MTD.

Not all analyses described in this SAP will necessarily be included in the CSR. Any analysis described in this SAP and not provided in the CSR would be available upon request. Not all displays will necessarily be created as a “static” display. Some may be incorporated into interactive display tools instead of or in addition to a static display.

4.2. Participant Dispositions

A detailed description of participant disposition will be provided at the end of the study.

Frequency counts and percentages of all participants screened, enrolled, randomized, and receiving at least 1 dose of study drug will be summarized by treatment group, if applicable. Of the randomized population, frequency counts and percentages of participants who completed the study, prematurely discontinued the study (and/or study drug), including reason for premature discontinuation, will be summarized by treatment group.

The study completion status for the randomized population is defined as follows: participants with status reported via eCRF as “Completed” at follow-up visit (Visit 801) will be considered as completers; otherwise, they will be considered as non-completers. A Kaplan-Meier analysis of time from randomization to premature discontinuation from study and/or study treatment by treatment group will be provided.

A listing of study disposition for all randomized participants will be provided at the final database lock.

4.3. Primary Endpoint Analysis

For primary disclosure including submission to the US FDA to support the registration of tirzepatide for chronic weight management, the primary efficacy assessment will be guided by the treatment regimen estimand conducted using the FAS. Assessment of the primary objective will be conducted with hybrid imputation of missing data (see Section 4.3.2.3).

For other purposes, the assessment of primary efficacy objective will be guided by the efficacy estimand using the EAS.

4.3.1. Definition of Endpoint

The primary efficacy measure will be percent change in body weight from randomization. The percent change in body weight at each nominal visit is defined as:

$$(\text{postbaseline body weight [kg]} - \text{baseline body weight [kg]}) / \text{baseline body weight [kg]} * 100\%.$$

Percent change in body weight will be summarized by treatment and nominal visit (week) from randomization (Week 36) to 88 weeks.

4.3.2. Main Analytical Approach

4.3.2.1. Analysis Related to the Treatment Regimen Estimand

The analysis related to the treatment regimen estimand will be conducted using the FAS.

The analysis for the mean percent change in body weight will be conducted utilizing ANCOVA. The response variable for the ANCOVA model will be percent change in body weight from randomization to Week 88. This model will include terms of treatment group, country/pooled country, sex, tirzepatide MTD dose at randomization, and body weight at randomization (Week 36) as covariates. The ANCOVA analysis will be conducted with multiple imputation of missing data guided by hybrid method at Week 88 (see Section 4.1 and Section 4.3.2.3 for details) and statistical inference over multiple imputation of missing data guided by Rubin (1987).

With the aid of the ANCOVA model, 2-sided 95% CI for mean percent change in body weight from baseline to the 88-week visit between tirzepatide MTD and placebo will be derived.

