## 6.3. Measures to Minimize Bias: Randomization and Blinding

This is a double-blind, randomized study.

Participants will undergo a 36-week open-label tirzepatide lead-in treatment period. Those who successfully complete the lead-in period (reaching either a 10-mg or 15-mg dose) will be randomized (1:1) in a double-blind fashion to either continue tirzepatide at MTD or switch to placebo for the duration of the double-blind treatment period. Assignment to treatment groups will be determined by a computer-generated random sequence using the interactive web-response system (IWRS).

The randomization will be stratified by country, sex (female, male), tirzepatide MTD dose at 36 weeks (10 mg versus 15 mg), and percent weight loss at 36 weeks (<10% versus  $\geq 10\%$ ).

Investigators, site staff, clinical monitors, and participants will remain blinded to the treatment assignments of the double-blinded treatment period until the study is complete.

Emergency unblinding for AEs may be performed through the IWRS. This option may be used ONLY if the participant's well-being requires knowledge of the participant's treatment assignment. All emergency unblinding events are recorded and reported by the IWRS.

If an investigator, site personnel performing assessments, or participant is unblinded, the participant must be discontinued from the study. In cases where there are ethical reasons to have the participant remain in the study, the investigator must obtain specific approval from a Lilly clinical research physician (CRP) for the participant to continue in the study.

In case of an emergency, the investigator has the sole responsibility for determining if unblinding of a participant's treatment assignment is warranted for medical management of the event. The participant's safety must always be the first consideration in making such a determination. If a participant's treatment assignment is unblinded, Lilly must be notified immediately. If the investigator decides that unblinding is warranted, it is the responsibility of the investigator to promptly document the decision and rationale and notify Lilly as soon as possible.

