#### **9.4.3. Efficacy Analyses**

##### **9.4.3.1. Primary Analyses**

There will be 2 estimands of interest in comparing efficacy of tirzepatide MTD with placebo.

For the FDA, the primary efficacy analysis will be guided by the “hybrid” estimand and will be conducted using the full analysis set (FAS). This assessment will analyze percent change in body weight from randomization (Week 36) to the 88-week visit using an analysis of covariance (ANCOVA). The model will include terms of treatment, stratification factors, and baseline body weight as a covariate. Missing data solely due to a pandemic or natural disaster (after other reasons for missing data are ruled out) will be considered missing at random, and missing data will be imputed using all nonmissing data of the primary outcome from the same treatment arm. Missing data of the primary outcome measurement due to all other Intercurrent Events will be imputed based on retrieved dropouts in the same treatment arm, defined as observed primary outcome measurements from participants in the same treatment group who had their efficacy assessed after early discontinuation of study drug. In cases where there are not enough retrieved dropouts to provide a reliable imputation model (for example, the model implemented by the SAS program does not converge), an alternative multiple imputation method with reference to the placebo group (that is, placebo multiple imputation) will be used. Analysis will be conducted with multiple imputations.

For all other purposes, the primary efficacy analysis will be guided by the “efficacy” estimand, which reflects efficacy prior to discontinuation of study drug and is conducted using the EAS. The primary analysis model will be an MMRM for body weight percent change over time. The response variable of MMRM will be the percent change in body weight from randomization obtained at each scheduled postbaseline visit. The independent variables are treatment group (tirzepatide MTD and placebo), visit, treatment-by-visit interaction, stratification factors, and baseline body weight as a covariate. An unstructured covariance structure will model the relationship of within-patient errors. The Kenward-Roger approximation will be used to estimate the denominator degrees of freedom.

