4.3.2.2. Analysis Related to the Efficacy Estimand

The analysis related to the efficacy estimand will be conducted utilizing data in the EAS.

For the mean percent body weight change from randomization, a MMRM will be conducted. Restricted maximum likelihood (REML) will be used to obtain model parameter estimates and

the Kenward-Roger option will be used to estimate the denominator degrees of freedom. The response variable of MMRM will be the percent change in body weight from baseline values obtained at each scheduled postbaseline visit.

For the MMRM model, the independent variables of analysis model are treatment group, visit, treatment-by-visit interaction, and stratification factors (country/pooled country, sex, and tirzepatide MTD dose at randomization) as fixed effects, and body weight at randomization (Week 36) as a covariate. An unstructured covariance structure will model relationship of within-patient errors. If this model fails to converge, the following variance covariance structures will be tested in order until convergence is achieved:

- heterogeneous Toeplitz
- heterogeneous first order autoregressive
- heterogeneous compound symmetry
- Toeplitz
- first order autoregressive, and
- compound symmetry.

The first covariance structure that converges will be used.

With the aid of the MMRM analysis, 2-sided 95% CIs for mean percent change in body weight from randomization to the 88-week visit for tirzepatide MTD compared to placebo will be derived and summarized. The resulting LSM estimates of mean percent change in body weight from baseline will be plotted by visit and by study treatment.

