4.3.2.4. Sensitivity Analysis

For submission of Study GPHN to the US FDA tirzepatide application for chronic weight management, additional sensitivity analyses of the primary efficacy outcomes will be conducted using the FAS and guided by the “treatment-regimen” estimand, which represents the efficacy irrespective of adherence to study drug. This assessment will analyze percent change in body weight obtained at the 88-week visit using an ANCOVA model. The terms of the model will be the same as specified in Section 4.3.2.1. These analyses are intended to assess the robustness of primary efficacy results using different missing data imputation methods:

- Retrieved dropout multiple imputation: Missing values of change in body weight at the 88-week visit will be imputed based on observed body weight change from randomization (Week 36) values at the visit from participants in the same treatment group who had their efficacy assessed after early discontinuation of study drug. In cases where there are not enough retrieved dropouts to provide a reliable imputation model (for example, the model implemented by the SAS program does not converge), the placebo multiple imputation method (described below) will be used.
- Placebo multiple imputation: Missing values of change in body weight at the 88-week visit will be imputed based on observed body weight change from randomization (Week 36) at the visit from participants in the placebo treatment group.
- 2-way tipping point analysis: The analysis will begin with the primary analysis aligned to treatment regimen estimand and adding positive and negative penalties simultaneously to both the tirzepatide MTD arm and the placebo arm, considering when results tip from superiority to inconclusive, and then considering the clinical plausibility of such scenarios.

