4.4.2. Key Secondary Efficacy Analyses Subject to Type 1 Error Rate Control

Table GPHN.4.2. Secondary Measures Controlled for Type 1 Error

Objectives	Relative to the efficacy measure:	Analysis conducted in a manner similar to	Additional Information
Tirzepatide MTD QW is superior to placebo:	Mean change in body weight (kg) from randomization (Week 36) to Week 88	For treatment regimen estimand: ANCOVA model described in Section 4.3.2.1. For efficacy estimand: MMRM model described in Section 4.3.2.2.	LSM estimates will be plotted by treatment through 88 weeks.
	Mean change in waist circumference (cm) from randomization (Week 36) to Week 88	For treatment regimen estimand: ANCOVA model with terms of treatment group, stratification factors, and corresponding value at randomization (Week 36) as covariates. For efficacy estimand: MMRM model with treatment group, visit, treatment-by-visit interaction, all stratification factors as fixed effects, and corresponding value at randomization (Week 36) as covariates.	LSM estimates will be plotted by treatment through 88 weeks. Refer to Sections 4.3.2.1 and 4.3.2.2 for analysis approach detail.
	Percentage of participants who maintain $\geq 80\%$ of the body weight lost during the 36 weeks of open-label period	For both treatment regimen and efficacy estimand: Logistic regression model will be conducted.	Refer to Section 4.4.1 for analysis approach detail.
Tirzepatide MTD QW is superior to placebo:	Percentage of study participants who achieve $\geq 5/10/15/20\%$ body weight reduction from Visit 2 (Week 0) to Week 88	For both treatment regimen and efficacy estimand: Logistic regression model will be used.	Refer to Section 4.4.1 for analysis approach detail.
	Time (in weeks), during the 52-week double-blind treatment period, to first occurrence of participants returning to $>95\%$ baseline weight for those who have already lost $\geq 5\%$ since Week 0	For both treatment regimen and efficacy estimand: Cox-proportional hazards model will be used with the terms of treatment group (tirzepatide MTD and placebo), country/pooled country, sex, tirzepatide MTD dose at randomization, and weight at randomization (Week 36) and at baseline (Week 0) as covariates.	Only for participants with at least 5% body weight loss during the open-label lead-in period. For treatment regimen estimand: the participant without event will be censored at Week 88.

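### The primary ANCOVA and MMRM drop the lead-in weight-loss stratum that the protocol's models keep, and the SAP gives no reason

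*SAP*

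**What the plan says.** Protocol Section 6.3 stratifies randomisation by country, sex, "tirzepatide MTD dose at 36 weeks (10 mg versus 15 mg), and percent weight loss at 36 weeks", the last split at 10%. Protocol Section 9.4.3.1 then says of the primary ANCOVA: "The model will include terms of treatment, stratification factors, and baseline body weight as a covariate". Of the primary MMRM it says: "The independent variables are treatment group (tirzepatide MTD and placebo), visit, treatment-by-visit interaction, stratification factors, and baseline body weight as a covariate". Neither sentence excepts a factor.

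SAP Section 4.1 gives a default covariate list for efficacy at 88 weeks that contains the factor: "tirzepatide MTD dose at randomization, percent weight loss at randomization and corresponding baseline value will be used as a covariate". That default yields wherever a section specifies something else, and the two primary sections do. For the ANCOVA, Section 4.3.2.1 says "This model will include terms of treatment group, country/pooled country, sex, tirzepatide MTD dose at randomization, and body weight at randomization (Week 36". For the MMRM, Section 4.3.2.2 names "stratification factors (country/pooled country, sex, and tirzepatide MTD dose at randomization) as fixed effects", with Week 36 weight as covariate. Percent weight loss is in neither list.

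The omission carries further:

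- Sensitivity analyses (Section 4.3.2.4): "The terms of the model will be the same as specified in Section 4.3.2.1".
- Change in body weight in kg (Table GPHN.4.2): "For treatment regimen estimand: ANCOVA model described in Section 4.3.2.1", with the matching reference to Section 4.3.2.2 for the MMRM.
- Percent change at Week 64 (same table): no covariates are named. The row refers to Section 4.4.1, which is written for categorical outcomes analysed by logistic regression and whose covariate lists also lack the stratum.

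The waist circumference row keeps the stratification factors.

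Item 4 of the Version 3 history states that weight-related endpoints exclude this factor. It presents this as a clarification, points to Section 4.4 and gives no reason. SAP Section 1 says changes from the protocol's analyses are in Section 4.9, which lists only two endpoints promoted to key secondary. Protocol Section 9.4.1 says that the SAP and the study report will describe such a change and its justification.

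**The concern.** A factor that randomisation has balanced should normally be in the model. Stratification removes its between-arm imbalance from the treatment estimate. A model that ignores it leaves its variance in the residual, so the model-based standard error is too large and the interval too wide.

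Week 36 weight does not make the stratum redundant. Lead-in loss is a function of Week 0 and Week 36 weight together, and the primary models hold only the second.

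Traceability is also at stake. The primary model under both estimands differs from the protocol's, this SAP does not say why, and no planned sensitivity analysis fits the protocol's model.

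The point is limited to the continuous models. The protocol names stratification factors only for those, so the logistic models in Section 4.4.1 are outside it.

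**Working it through.** **Inputs from the documents** (protocol Section 9.2, SAP Section 5): 300 randomised per arm, 25% dropout, common SD 8%, difference 6%, two-sided alpha 0.05. Evaluable per arm: 300 × (1 − 0.25) = 225.

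**Assumed inputs.** The documents give neither the share p of participants in the <10% stratum nor the difference d in outcome between strata. I take p from 10% to 30% and d from 2 to 6 percentage points.

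**1. The plan's power.**
SE = 8 × √(2/225) = 0.754. The 95% half-width is 1.96 × 0.754 = 1.478. Then 6/0.754 = 7.96, and power is above 99.99% (normal approximation and exact t-test). The stated figure of more than 90% is reproduced, and the omission does not threaten it.

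**2. Size of the overstatement.**
With the same stratum difference in both arms, R² = p(1 − p)d²/64, and the SE without the stratum is too large by 1/√(1 − R²) − 1. With the difference in one arm only, the pooled effect is d/2, so d/2 replaces d.

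| p | d | R², both arms | SE overstated | Half-width with stratum | R², one arm | SE overstated | Half-width with stratum |
|---|---|---|---|---|---|---|---|
| 10% | 2 | 0.0056 | 0.28% | 1.474 | 0.0014 | 0.07% | 1.477 |
| 20% | 4 | 0.040 | 2.06% | 1.448 | 0.010 | 0.50% | 1.471 |
| 30% | 6 | 0.118 | 6.49% | 1.388 | 0.0295 | 1.51% | 1.456 |

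Example: 0.2 × 0.8 × 16/64 = 0.04, and 1/√0.96 − 1 = 2.06%.

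**3. Simulation check.**
4,000 runs per case; 600 randomised in stratified blocks of 4 (assumed); 25% random dropout; sex, dose, country and Week 36 weight in the model.

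| Case | Mean SE without stratum | With stratum | Ratio |
|---|---|---|---|
| p = 20%, d = 4, both arms | 0.757 | 0.742 | 1.020 |
| p = 20%, d = 4, one arm | 0.756 | 0.753 | 1.005 |
| p = 30%, d = 6, both arms | 0.757 | 0.711 | 1.065 |
| p = 30%, d = 6, one arm | 0.756 | 0.745 | 1.015 |
| p = 20%, d = +4 and −4 by arm | 0.757 | 0.758 | 1.000 |
| p = 20%, d = 4, both arms, stratum correlated with dose and Week 36 weight | 0.755 | 0.742 | 1.018 |

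The last case assumes 25% versus 10% on 10 mg and a 0.8 SD shift in Week 36 weight. Bias was at most 0.022 points in every case.

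**4. Type I error with the stratum omitted.**
After dropout it was 0.048 at R² = 0.04 and 0.043 at R² = 0.118 (Monte Carlo error 0.003). A separate simulation without dropout (p = 20%, 8,000 runs per R²) gave 0.052, 0.043, 0.042 and 0.029 at R² = 0, 0.05, 0.10 and 0.20, against 0.049 to 0.053 with the stratum included. Any shift is conservative. In the central case after dropout it cannot be told apart from 0.05.

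**The case against.** The best defence is that the exclusion is deliberate and disclosed. The Version 3 history separates weight-related endpoints from the others, and the models follow that rule. The Section 4.1 default gives way to specific text, so the SAP does not contradict itself. The history also refers Version 2 details to a record that is not part of these documents, and the study report is not available, so a reason may exist elsewhere. All of this stands. It does not supply the justification that the protocol says the SAP will contain, or the entry that SAP Section 1 sends the reader to find in Section 4.9.

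Second, Section 4.7.2.1 plans a model with each subgroup variable as a covariate, and lead-in weight loss split at 10% is one of them. That may reproduce the protocol's covariate set under both estimands. But it is presented as a subgroup analysis and takes its details from Section 4.4.1. It is not designated as a check on the primary result.

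Third, the effect is small and rests on assumptions. The 6.5% ceiling needs a stratum difference of 6 points in both arms, as large as the assumed treatment effect. The protocol's one related figure, that nearly half of Phase 2 participants at the two higher doses lost at least 10%, comes from patients with type 2 diabetes. It suggests a <10% share outside my range; at p = 50% and d = 4, R² = 0.0625 and the overstatement is 3.3%. The simulation used complete cases, not the planned multiple imputation or MMRM. These points limit the size of the claim, not its direction.

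No reason in the documents favours leaving out a factor on which randomisation was stratified.

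**Conclusion.** The concern holds. Both SAP primary models drop one stratification factor that the protocol's models include. This SAP gives no reason, and Section 4.9 is silent.

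The consequence is modest. There is no bias, no inflation of type I error and no threat to power. The central estimate is a standard error about 2% too large, with both stratum share and effect assumed. It is about 0.5% if only one arm shows the effect and about zero if the effects have opposite signs. The change should be made because it is a nearly free gain in precision and brings the primary model back into line with the protocol, not because the result depends on it.

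**What to change.** Add the percent-weight-loss stratum (<10% versus ≥10%) to the models in SAP Sections 4.3.2.1 and 4.3.2.2. The kg row of Table GPHN.4.2 and the sensitivity analyses in Section 4.3.2.4 then inherit it. Point the Week 64 row to Sections 4.3.2.1 and 4.3.2.2 instead of 4.4.1, so that its covariates are defined and include the stratum.

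If the sponsor keeps the exclusion, state it with its reason in Section 4.9 and add the protocol's model, with all stratification factors, as a sensitivity analysis in Section 4.3.2.4. The Week 64 reference needs correcting either way.

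The cost is SAP wording and one degree of freedom for a binary covariate already held for randomisation. No new data are needed.
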